5.4.2 Secondary Efficacy Endpoints

Adjustment for multiplicity will be done as described in the protocol. Further details can be found in section [5.6.4](#).

5.4.2.1 Proportion of days in remission

The endpoint is the proportion of days in remission as compared to the number of days in remission described in the protocol section 11.3.3.5. Analysis and sensitivity analysis are also different as compared to the protocol. See section [5.7](#) for details regarding changes to the protocol.

The number of days in remission will be calculated as the sum of days where the subject is in remission periods as defined in [Table 1](#). The proportion of days in remission will be calculated

as the number of days in remission divided by the length of the maintenance phase in days. The proportion of days in remission will be summarised by treatment group.

[figure not shown]
Multiple imputation:

Multiple imputation of data for withdrawn subjects will be done using 100 imputations (seed=20910158). In order not to favour any treatment arm, the imputation approach will depend on whether the subject's reason for withdrawal potentially is related to IMP or not.

For the imputation, the length of the maintenance phase is assumed to be 52 weeks, corresponding to 364 days.

Imputation for subjects withdrawn with reasons 'withdrawal by subject' or 'lost to follow up': This approach assumes that the unobserved remission pattern for withdrawn subjects will be like the pattern observed for subjects in the same treatment group completing the maintenance phase. An example can be found in [Figure 1](#) and the described below.

Figure 1: Example of imputation for a subject withdrawing from trial due to lost to follow-up or withdrawal by subject

Imputation steps:

1. For a withdrawn subject the 'number of unobserved days' will be computed as 364 minus the length of the subject's maintenance phase. This 'number of unobserved days' (e.g.; 64) will be used in step 2.

Trial ID: LP0053-1004	Date: 15-JUL-2019	Version: 1.0 Page 14 of 177
-----------------------	-------------------	--------------------------------

2. For the sub-set of subjects, that are in the same treatment group as the withdrawn subject and completed their maintenance phase, the proportion of days in remission will be calculated for the last part in their maintenance phase lasting 'number of days unobserved' (e.g.; 64).
3. A single proportion of days in remission will be randomly sampled from the proportions calculated in step 2. This will be called the 'sampled proportion' (e.g.; 95%)
4. For the withdrawn subject, the number of days in remission for the missing period will be estimated by multiplying the 'sampled proportion' by the 'number of unobserved days' (e.g.; 0.95×64).
5. For the withdrawn subject, the proportion of days in remission will be calculated by summing the observed number of days in remission and the estimated number of days in remission (from step 4) and dividing by 364.
6. Steps 1 to 5 will be repeated 100 times for each withdrawn subject to form 100 complete datasets.

Imputation for subjects withdrawn with reasons 'adverse event', 'death', 'lack of efficacy', or 'subject not achieving clear or almost clear after treatment of relapse':

This approach assumes that the unobserved part of the trial for subjects withdrawn due to these reasons, would have been similar to the observed part of the trial for the subjects withdrawing for the same four reasons regardless of treatment arm. An example can be found in [Figure 2](#) and described in the imputation step below.

[figure not shown]
Imputation steps:

1. For a withdrawn subject the 'number of unobserved days' (e.g.; 64) will be computed as 364 minus the length of the subject's maintenance phase.
2. For the sub-set of subjects withdrawn due to 'adverse event', 'death', 'lack of efficacy', or 'subject not achieving clear or almost clear after treatment of relapse', the proportion of days in remission will be calculated.
3. A single proportion of days in remission will be randomly sampled from the proportions in step 2. This will be called the 'sampled proportion' (e.g.; 50%)

4. For the withdrawn subject, the number of days in remission for the missing period will be estimated by multiplying the 'sampled proportion' by the 'number of unobserved days' (e.g.; $0.50*64$).
5. For the withdrawn subject, the proportion of days in remission will be calculated by summing the observed number of days in remission and the estimated number of days in remission (from step 4) and dividing by 364.
6. Steps 1 to 5 will be repeated 100 times for each withdrawn subject to form 100 complete datasets.

Figure 2: Example of imputation for a subject withdrawing from trial due to AE, death, lack of efficacy, or subject not clear or almost clear after treatment of relapse

Imputation for subjects leaving the trial due to other reasons:

For cases with withdrawal reason specified as 'Other', the details will be revised on a blinded manner, selecting and documenting the imputation approach in the Analysis Set Definition Document.

Statistical analysis:

For each of the 100 complete data sets, the difference in proportion of days in remission between treatment groups will be analysed by means of an analysis of variance (ANOVA) model as described in the protocol section 11.3.3.5. The estimates and standard errors from

Trial ID: LP0053-1004	Date: 15-JUL-2019	Version: 1.0 Page 16 of 177
-----------------------	-------------------	--------------------------------

the 100 analyses will be pooled to one estimated treatment difference and associated standard error using Rubin's rule to draw inference. From these pooled estimates, the 95% CI for the treatment difference will be calculated. The p-value for treatment difference will be calculated using a two-tailed Student's t-test based on the pooled estimates.

A histogram with a density curve of proportion of days in remission by treatment group will be presented.

Number of days in remission between relapses will be plotted by treatment group.

Sensitivity analysis:

An additional sensitivity analysis will be performed assuming that after the subjects withdrew the pattern of remission will be as if the subject was not treated. This will be done as described above, however in step 2 of the sub-set of subjects will be subjects treated with vehicle.

Further details for tables, figures and listings are given in [Appendix I](#) and [Appendix II](#).

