11.1 Determination of Sample Size

For subjects with psoriasis vulgaris, the number of relapses per year is assumed to be between 4 and 8. We assume that the time to event (first relapse) is a Poisson process, i.e. that events occur continuously and independently at a constant rate. Then the time between events is given by the exponential distribution. Time to event is analysed by means of the hazard function, which can be thought of as the probability of experiencing an event now if you have not experienced one already. [Table 16](#) shows the mean and median waiting times as well as hazards according to number of relapses per year.

Table 16: Mean and median waiting times and hazards according to number of relapses per year

	Number of relapses per year		
	4	6	8
Mean waiting time (weeks)	13.00	8.67	6.50
Median waiting time (weeks)	9.01	6.01	4.51
Hazard	0.077	0.115	0.154

The drop-out rate observed in a long-term trial with calcipotriol/BDP ointment (MCB 0102 INT) was about 30 % over 52 weeks. Assuming an exponential decline this corresponds to a median waiting time for drop out at about 101 weeks. We assume that the same will be the case in this trial and that between 4 to 8 relapses will occur per year in the vehicle group.

A 30 percent reduction in hazard, i.e. a hazard ratio of 0.7 for active treatment group relative to vehicle group is considered to be of clinical interest.

With the above assumptions it follows using a two sample survival test that for detecting a hazard ratio of 0.7 for active treatment group relative to vehicle group, between 178 and 190 subjects per group are needed in order to obtain a power of 90% for a 5% significance level. Thus, 380 subjects should be randomised.

In previous trials in similar populations, approximately 48% subjects treated with LEO 90100 aerosol foam achieved treatment success after 4 weeks of treatment. Assuming a binomial distribution with 48 % probability of success it is estimated that 832 subjects should be included in the trial in order to have 90 % probability of achieving at least 380 subjects to be randomised.

For the HPA axis testing, the aim is to achieve approximately 25 subjects undergoing HPA axis testing after 52 weeks of exposure.

The total number of subjects treated in the trial should also be sufficient to comply with ICH E1 regarding long-term safety. The aim is to achieve at least 300 subjects with 26 weeks of exposure and at least 100 subjects with 52 weeks of exposure.

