5.5.9	Laboratory Data	36
5.6	General Principles	37
5.6.1	Pooling of Trial Sites	37
5.6.2	Handling of Drop-outs and Missing Values	38
5.6.3	Incomplete dates	38
5.6.4	Multiplicity adjustment	38
5.6.5	Treatment Labels	39
5.7	Changes to the analyses described in the protocol	40
	Appendix I	47
	Appendix II	67

Trial ID: LP0053-1004	Date: 15-JUL-2019	Version: 1.0 Page 6 of 177
------------------------------	--------------------------	-------------------------------

3 List of Abbreviations

ACTH	Adrenocorticotropic Hormone
AE	Adverse Event
ATC	Anatomical Therapeutic Chemical
BSA	Body Surface Area
CPM	Clinical Project Manager
CPMP	Committee for Proprietary Medicinal Products
CRA	Clinical Research Associate
CRF	Case Report Form
CRO	Contract Research Organisation
DK	Denmark
DLQI	Dermatology Life Quality Index
eCRF	Electronic Case Report Form
eDiary	Electronic Diary
EU	European Union
GCP	Good Clinical Practice
ICH	International Conference on Harmonisation
IEC	Independent Ethics Committee
IMP	Investigational Product
IRB	Institutional Review Board
m-PASI	Modified Psoriasis Area Severity Index
MedDRA	Medical Dictionary for Regulatory Activities
MMRM	Mixed effect Model Repeat Measurement
ML	Maximum Likelihood
PASI	Psoriasis Area Severity Index
PASI 75	A 75% reduction in the modified Psoriasis Area Severity Index
PGA	Physician's Global Assessment of Disease Severity
PRO	Patient Reported Outcome
PSI	Psoriasis Symptom Inventory
REML	Restricted Maximum Likelihood
SAE	Serious Adverse Event

SAP	Statistical Analysis Plan
SD	Standard Deviation
SGA	Subject's global assessment of disease severity
SOC	System Organ Class
SOP	Standard Operating Procedure
UNS	Unscheduled Visit

4 Introduction

The statistical analysis will be performed as outlined in the Clinical Trial Protocol including amendments. This statistical analysis plan, prepared before the unblinding of the trial, but after the blind review of the data, contains a more technical and detailed elaboration of some points in the statistical analysis described in the Clinical Trial Protocol. Deviations from the planned data presentation and analysis are also described in section [5.7](#). Furthermore, the analysis sets, which are to be used for the statistical analysis, are presented.

5 Statistical Analysis

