5.6.4 Multiplicity adjustment

To control the overall type 1 error rate, the analyses of the primary and secondary endpoints will follow the hierarchical testing procedure outlined in [Figure 3](#). The hypotheses relating to the two secondary endpoints cannot be rejected unless the hypothesis relating to the primary endpoint is also rejected.

Figure 3: Testing procedure for primary and secondary endpoints

The procedure will be as follows:

Time to first relapse between LEO 90100 and vehicle is evaluated at a 5% significance level. If the test is significant, the significance level will be split between the analyses of the two secondary endpoints using the Holm Bonferroni method to adjust for multiplicity. Hence the proportion of days in remission and the number of relapses during the maintenance phase between LEO 90100 and vehicle will be tested in parallel at a 2.5% significance level.

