Shell 98: Subjects with serum cortisol concentration \leq 18 mcg/dL at both 30 and 60 minutes after ACTH-challenge in maintenance phase; HPA analysis set.....	173
Shell 99: Individual data for subjects with serum cortisol concentration \leq 18 mcg/dL at either 30 minutes or 60 minutes after ACTH-challenge: HPA analysis set.....	175
Shell 100: Serum-cortisol concentration at time 0 and at 30 and at 60 minutes after ACTH-challenge in the follow-up phase: HPA analysis set.....	176
Shell 101: Summary of rebounds occurring within 2 months after discontinuing open-label phase treatment or relapse treatment: safety analysis set.....	177
Shell 102: Summary of rebounds occurring within 2 months after discontinuing of maintenance treatment: safety analysis set.....	177

Shell 1: Disposition of subjects in the open-label phase: enrolled subjects

Open-label LEO 90100 (n=xxx)		
	Visit 2 (Week 4) attendance	
	N (%)	Yes / No
Enrolled subjects	xx (xx.x)	xx / xx
Randomised subjects	xx (xx.x)	xx / xx
Withdrawn from trial during open-label phase	xx (xx.x)	xx / xx
Adverse event	xx (xx.x)	xx / xx
Death	xx (xx.x)	xx / xx
Lost to follow-up	xx (xx.x)	xx / xx
Withdrawal by subject	xx (xx.x)	xx / xx
Lack of efficacy	xx (xx.x)	xx / xx
Subject did not achieve treatment success after initial 4 weeks treatment	xx (xx.x)	xx / xx
Other	xx (xx.x)	xx / xx

N: Number of subjects, %: Percentage of subjects.

Shell 2: Disposition of subjects in the randomised phase: randomised subjects

	All randomised subjects (n=xxx)	LEO 90100 (n=xxx)	Vehicle (n=xxx)
	N (%)	N (%)	N (%)
Randomised subjects	xx (100.0)	xx (100.0)	xx (100.0)
Full analysis set	xx (xx.x)	xx (xx.x)	xx (xx.x)
Safety analysis set	xx (xx.x)	xx (xx.x)	xx (xx.x)
Per protocol analysis set	xx (xx.x)	xx (xx.x)	xx (xx.x)
Withdrawn from trial during randomised phase	xx (xx.x)	xx (xx.x)	xx (xx.x)
Adverse event	xx (xx.x)	xx (xx.x)	xx (xx.x)
Death	xx (xx.x)	xx (xx.x)	xx (xx.x)
Lost to follow-up	xx (xx.x)	xx (xx.x)	xx (xx.x)
Withdrawal by subject	xx (xx.x)	xx (xx.x)	xx (xx.x)
Lack of efficacy	xx (xx.x)	xx (xx.x)	xx (xx.x)
Subject did not achieve treatment success after initial 4 weeks treatment ¹	xx (xx.x)	xx (xx.x)	xx (xx.x)
Subject not clear or almost clear after treatment of relapse	xx (xx.x)	xx (xx.x)	xx (xx.x)
Other	xx (xx.x)	xx (xx.x)	xx (xx.x)

N: Number of subjects, %: Percentage of subjects.

1) Subjects randomised in error.

Shell 3: Reasons for leaving the trial during the open-label phase by last visit attended: enrolled subjects

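### Does the donor-based imputation for proportion of days in remission give a standard error that has to be corrected?

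*SAP*

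**What the plan says.** SAP 5.4.2.1 uses 100 imputations and a 364-day maintenance phase, with two donor schemes.

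- **Withdrawal by subject, lost to follow-up.** The donors are subjects "in the same treatment group completing the maintenance phase". One donor's proportion of days in remission, taken over the matching last stretch of the phase, is sampled.
- **Adverse event, death, lack of efficacy, failed relapse treatment.** The unobserved time "would have been similar to the observed part of the trial for the subjects withdrawing for the same four reasons regardless of treatment arm". One proportion is sampled from that combined list.

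For any other reason, "the details will be revised on a blinded manner, selecting and documenting the imputation approach in the Analysis Set Definition Document". The 100 ANOVA results "will be pooled to one estimated treatment difference and associated standard error using" Rubin's rule, and the confidence interval and t-test follow from that standard error. The one sensitivity analysis switches to vehicle donors and keeps the same variance method.

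Under SAP 5.6.4 the two secondary endpoints are reached only if the primary test succeeds; they then "will be tested in parallel at a 2.5% significance level". According to its Introduction, the SAP was "prepared before the unblinding of the trial, but after the blind review of the data". Shell 2 tabulates withdrawals by reason and arm, including "Subject not clear or almost clear after treatment of relapse".

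**The concern.** Rubin's rule assumes that the imputations carry all the uncertainty about the missing values. Here they do not, and the two schemes fail in opposite directions.

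With same-arm completer donors, the same list serves all 100 imputations, so the chance make-up of that list never enters the between-imputation variance. The standard error comes out too small and the test can reject too often.

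With the list pooled across arms, the donor mean enters both arms and mostly drops out of the difference. Rubin's rule still counts the spread of the draws, so the standard error comes out too large and power is lost.

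The interval alone does not show a reader which case applies. The endpoint carries formal alpha, and the SAP plans no check of its standard error. For the other secondary endpoint it does plan one: a negative binomial model in case the Poisson model misses overdispersion.

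**Working it through.** **Inputs from the documents.** Randomised subjects: 132+55+52+68+56+68+114 = 545, about 272 per arm (SAP Table 8). Allocation 1:1 (Protocol 6.3). In Protocol 11.1 "the number of relapses per year is assumed to be between 4 and 8", drop-out is about 30% over 52 weeks (taken from a long-term ointment trial), and the target hazard ratio is 0.7. Rescue lasts 4 weeks.

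**Assumed, because the documents are silent:** the split of withdrawals by reason, and the between-subject spread in relapse rate (gamma frailty).

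**The plan's own figure.** No SD, standard error or power is stated for this endpoint. The primary sample size can be reproduced.

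- Events = 4(1.960+1.282)²/(ln 0.7)² = 331.
- Drop-out hazard δ = −ln(0.7)/52 = 0.00686 per week.
- Event probability = λ/(λ+δ) × [1−exp(−52(λ+δ))].
- At 4 relapses a year: 0.906 (vehicle) and 0.849 (active), mean 0.8778; 331/(2×0.8778) = 188.5 per group.
- At 8 a year the mean is 0.9474, giving 174.7.
- Freedman's formula gives 192.5 and 178.4. The protocol states 190 and 178, so the planning inputs are read correctly.

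**Direction, in the limiting case** where a fraction f of whole outcomes is missing. Let s² be the outcome variance and n the arm size. Rubin's variance per arm is s²/n within plus f·s²/n between, that is (1+f)s²/n.

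- Same-arm donors: the true variance is s²/[n(1−f)], so the SE ratio is √[(1+f)(1−f)]. This is √0.91 = 0.954 at f = 0.3, √0.84 = 0.917 at 0.4 and √0.75 = 0.866 at 0.5.
- Shared donors, equal f in both arms: the donor mean cancels and the true variance is (1−f)s²/n per arm. The ratio is √[(1+f)/(1−f)], above 1. Observed days are kept in the real algorithm, so the excess there is smaller.

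**Simulation of the SAP algorithm**: 272 per arm, 6 relapses a year, frailty variance 0.5, no true difference, no covariates, 3,000 trials, Monte Carlo error about 1.3% of the ratio.

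| Withdrawals | Rubin SE / true SD | Rejects at 2.5% | Rejects at 5% |
|---|---|---|---|
| none | 1.02 | 2.8% | 4.9% |
| 30% completer-donor | 0.93 | 3.9% | 6.9% |
| 50% completer-donor | 0.88 | 4.6% | 8.1% |
| 24% failure-type | 1.07 | 1.4% | 3.3% |
| 40% failure-type | 1.16 | 0.8% | 2.3% |
| 27% completer-donor + 20% failure-type | 1.03 | 2.2% | 4.6% |

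Other simulations gave 0.97 and 1.00 at 30% completer-donor exits, 0.91 to 0.92 at 40%, 1.10 at 24% failure exits, and 1.02 for a 21%/9% mix. Without frailty the ratio was 0.91 at 50% completer-donor exits and 1.28 at 38% failure exits. A 27%/18% mix with 190 per arm and 6 v 4.2 relapses a year gave 1.10.

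**Total drop-out held at 30%**, pooled sites in the model, 4 to 8 relapses a year, frailty variance 0 to 1. With failure exits of 3/10/20/30% the ratios are 0.95-1.02, 1.00-1.07, 1.05-1.16 and 1.10-1.26. Rejection at nominal 5% is 4.7-6.2, 3.5-5.2, 2.1-4.0 and 1.4-3.2%.

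**Power at 2.5%**, Rubin v a bootstrap of the whole procedure, same four shares, 6 relapses a year, frailty 0.5.

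- HR 0.7: 96.7 v 96.2, 97.3 v 97.6, 95.2 v 96.8, 93.6 v 96.0%. The largest gap is 96.0−93.6 = 2.4 points.
- HR 0.8: 64.7 v 62.4, 61.4 v 62.2, 57.9 v 62.7, 50.2 v 60.8%.

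**What the remedies deliver.**

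- *Redrawing the completer list by bootstrap in each imputation* moved the ratio only from about 0.91 to 0.95 at 40%.
- *Bootstrapping subjects and re-imputing* tracks the true SD (0.0139 v 0.0141 with 40% failure exits; Rubin 0.0164). Yet 0.0139 is no larger than the bootstrap SE with no withdrawals, 0.0140: losing 40% of subjects adds no uncertainty.
- *A blinded check with dummy arm labels* gave 10th-90th percentile ratios of 0.95-1.00, 0.98-1.04, 1.03-1.11 and 1.08-1.16 for the four shares at HR 0.7. At the lower two it often cannot be told from about right.

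**The case for a change.** The best case for acting is that both mechanisms are plain in the text and reproduce in simulation, and that failure exits need not be rare. Protocol 7.9 removes anyone not clear or almost clear after four weeks of relapse treatment, and with 4 to 8 relapses a year a subject may meet that rule repeatedly. At a hazard ratio of 0.8 with 30% failure exits, Rubin's interval costs about ten points of power (50.2 v 60.8%). At the other extreme, 40-50% completer-donor withdrawals give about 7-8.5% rejection at nominal 5% and roughly 4-5% at 2.5%. A dummy-label check needs no treatment codes and could be recorded with the other blinded imputation decisions.

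The mechanism and both directions stand. It also stands that excess false positives cannot be called small without condition: that holds at about 30% total drop-out, not when withdrawals are far more numerous and almost all by subject or lost to follow-up.

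What does not follow is a change. A check without a threshold and a named alternative test decides nothing. The bootstrap interval answers a question on which statisticians reasonably differ: whether a standard error should fail to grow, or even shrink, as data go missing because both arms borrow from one list. The SAP pooled that list deliberately, so as not to favour either arm.

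**Conclusion.** No change to the plan. Rubin's standard error is approximate here, and the approximation is a fair trade-off. At the planned 30% drop-out and with failure exits up to 10%, it lies within about 7% of the true SD. Larger errors need either mostly failure exits, where the test is conservative, or 40-50% completer-donor withdrawals, where it is liberal. The point estimate is the same under every option considered, and at HR 0.7 the test almost always reaches the same answer.

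The gatekeeping limits the harm further. A liberal test here matters only if treatment is shown to delay first relapse and yet has no effect on days in remission. Shell 2 already reports withdrawals by reason and arm, so a reader who meets a p-value near 0.025 can judge which way the interval leans.

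This rests on scenario values. The withdrawal split and frailty are assumed, and the 30% comes from another trial. The 545 counts randomised subjects, while the analysis uses the slightly narrower full analysis set. The Analysis Set Definition Document was not available. A correction would be worth making only with a decision rule fixed before unblinding, and no alternative standard error is clearly better across these scenarios.

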5.4.2.2 Number of relapses during maintenance phase

The number of relapses will be analysed using a Poisson regression model with treatment group, pooled sites, and disease severity at maintenance baseline as factors, subject as random effect, and time at risk as an offset. REML will be used for estimation. Maintenance baseline is used in the model as compared to baseline at visit 1. See section [5.7](#) for details regarding changes as compared to the protocol.

Number of relapses will be summarised by treatment group. Rates (number of relapses divided by patient years of exposure multiplied by 100) will also be presented.

In addition, the distribution of the relapse rate by treatment group will be presented.

Sensitivity analysis:

The number of relapses will be analysed with a negative binomial regression model with treatment group, pooled sites, and disease severity at maintenance baseline as factors, subject as random effect, and time at risk as an offset. REML will be used for estimation. The purpose of this sensitivity analysis is to account for potential overdispersion in data, which is not adjusted for in the Poisson model.

See section [5.7](#) for details regarding changes as compared to the protocol.

Trial ID: LP0053-1004	Date: 15-JUL-2019	Version: 1.0 Page 17 of 177
-----------------------	-------------------	--------------------------------

More details for the tables and listings can be found in [Appendix I](#) and [Appendix II](#).

